## 1. SYNOPSIS

Name of Investigational Product:	RLF-100
Name of Active Ingredient:	Aviptadil
Reference Product(s):	Vasoactive Intestinal Polypeptide (synthetic)
Title of Study:	RLF-100 for the Treatment of Critical COVID-19 with Respiratory Failure
Phase of Development:	Phase 2b/3
Study Site(s):	Multi Center: University of Miami, UC Irvine, Houston Methodist, and others
Total Participant Number:	198 evaluable (mITT) subjects with Critical COVID-19 on mechanical ventilation (for <8 days), non-invasive ventilation or high flow rate nasal cannula at minimum 20L flow and 50% FIO 2
Study Duration:	60-day total follow-up
Background and Rationale:	The research to be conducted under this protocol references Phase 1 research conducted under IND 52,088 in which Vasoactive Intestinal Polypeptide (VIP) has previously shown suggestions of efficacy in the treatment of ARDS related to sepsis, pulmonary arterial hypertension and other respiratory disorders.
Objectives:	To demonstrate the efficacy of RLF-100 in improving survival and reducing respiratory distress / requirement for mechanical ventilation in patients with Critical (NIH/FDA definition) COVID-19 receiving maximum standard of care other than extracorporeal membrane oxygenation (ECMO).
Endpoint(s):	
Primary Outcome Measure:
 
 
1) Cumulative distribution of the time to respiratory failure resolution with concurrent survival through Day 28.
 
 
Key Secondary Measure:
 
 
2) NIAID Ordinal Scale for Clinical Improvement (Scores 6-8) through Day 28
 
 
Secondary Outcome Measures (through Day 28 unless otherwise specified):
 
 
3) Survival lifetable through Day 28 and through Day 60
 
4) Time to ICU discharge
 
5) Time on invasive mechanical ventilation
 
6) Time on non-invasive ventilation
 
7) Time to discharge alive
 
8) Multi-organ failure free days
 
9) NIAID Area under the curve (AUC)
 
 
Other Outcome Measures (through Day 28):
 
 
10) Respiratory Distress while on mechanical ventilation: Blood PaO2/FiO2 ratio [Time Frame: enrollment through extubation]
 
11) Oxygenation Index
 
12) Improvement in chest x-ray
 
13) IL-6, TNF<math>\alpha</math> and other inflammatory markers
 

Study Design:	Patients with Critical COVID-19 who are receiving Maximal Standard of Care (SOC) therapy that includes non-invasive high pressure or mechanical ventilation will be randomized to intravenous Aviptadil + Maximal SOC vs. Placebo + Maximal SOC, escalating from 50 pmol/kg/hr to 150 pmol/kg/hr.
Inclusion Criteria:	
 
1) Primary Cohort: Critical COVID-19 (test positive in past 7 days) with respiratory failure by NIH/FDA definition requiring either mechanical ventilation, non-invasive ventilation or high flow rate nasal cannula at minimum 20L flow and 50% FIO2. No more than 7 days of mechanical ventilation.
 
2) Physician commitment to maximum Standard of Care as deemed necessary
 

Exclusion criteria:	
 
1) Pregnancy
 
2) Age <18 years
 
3) Mechanical ventilation for more than 7 days in primary cohort.
 
4) Mean Arterial Pressure < 65 mm Hg with use of pressor per ICU protocol
 
5) Irreversible condition (other than COVID-19) with projected fatal course
 
6) ECMO
 
7) Current or recent (within 30 d) enrollment in another investigational trial of anti-IL6 drug or immunomodulator drug;
 
8) Active diagnosis of Acquired immune deficiency syndrome;
 
9) Transplant patients currently immunosuppressed;
 
10) Chemotherapy-induced neutropenia (granulocyte count <1000/mm^3);
 
11) Cardiogenic shock; congestive heart failure – NYHA Class 3 or 4;
 
12) Recent myocardial infarction – within last 6 months and troponin > 0.5
 
13) Anuria (urine output < 50 ml/d) or other signs of multi-organ failure
 
14) Severe liver disease with portal hypertension or bilirubin 4.0 or higher;
 
15) Recent stroke or head trauma within last 12 months
 
16) Increased intracranial pressure, or other serious neurologic disorder;
 
17) Liquid diarrhea more than 3x/day; defined as more than 3 non-bloody watery stools within a 24-hour period, requiring additional fluid and electrolyte supplementation
 

Safety Assessments:	A safety analysis was conducted by the Data Monitoring Committee at 21 patients. All patients will be surveilled for Serious Adverse Events (SAE). All SAEs will be reported to independent Data Safety Monitoring Board and to FDA
Dosage, Route of Administration, and Schedule:	Three escalating doses of RLF-100 (Aviptadil): 50, 100, and 150 pmol/kg/hour or placebo administered over 12 hours via IV infusion on successive days. If side effects cannot be managed with ICU protocol, dose reduced or halted.
Statistical Methods:	Primary endpoint (cumulative distribution of the time to respiratory failure resolution) with concurrent survival through Day 28 will be displayed by a lifetable through Day 28 and analyzed using a proportional hazard model analysis containing 4 pre-defined baseline covariates and randomized treatment group (primary) as well as an unstratified log rank test (secondary). Primary endpoint ascertainment requires that recovery from respiratory failure be maintained for at least 7 days without relapse. The cumulative distribution will be constructed through Day 28 with no censoring for death or withdrawal; such patients will be regarded as failures. Other time to event outcomes will be similarly analyzed with the exception of survival which will censor for any withdrawals. NIAID Score will be analyzed by carrying forward any early deaths through Day 28; other ordinal and continuous outcomes will be assessed by mixed model repeated measures through Day 28. The primary analysis will be based on the modified intent-to-treat (mITT) population to be based on all treated patients.

Sample Size Calculation:	For the primary efficacy endpoint, assuming a 40% success percent in the placebo group by Day 28 and a 62% success percent in the RLF-100 group by Day 28, for log rank test with two-sided overall 5% Type I error and 81% power, the sample size to detect a 22% absolute improvement in the percent achieving respiratory failure resolution by Day 28 (from 40% to 62%) is 198 subjects in the primary analysis group (2:1 randomization favoring the RLF-100 group). A 20% absolute advantage in the percent achieving respiratory failure resolution by Day 28 is deemed to be clinically meaningful.
Interim Analyses	An interim look for safety and futility will be conducted once the first 21 randomized subjects complete Day 7. A second interim look for safety, futility, and efficacy will be conducted once the next 81 subjects complete Day 28 but the study will not be prematurely stopped for efficacy.
Maintenance of Study Blind	Investigational drug will be administered in identical infusion bags, labeled by the hospital research pharmacist who is the only unblinded member of the study site. ICU personnel are entirely masked as to treatment assignment, as are patients. Even in the event of unintentional unblinding because of differential efficacy or safety of the investigational medicinal products (drug and placebo), the randomization scheme prevents staff from knowing the next treatment assignment. Moreover, the primary and declared secondary endpoints are not subject to interpretation by ICU staff.

## 5. LIST OF ABBREVIATIONS

AA	Amino Acid
ALI	Acute Lung Injury
ARDS	Associated Acute Respiratory Distress Syndrome
COVID-19	Corona Virus Disease 2019
ECMO	Extracorporeal membrane Oxygenation
ED	Erectile Dysfunction
EMR	Electronic Medical Record
Fas	Cell Surface Death Receptor
HCl	Hydrogen Chloride
ICU	Intensive Care Unit
ITT	Intent-to-Treat
IL	Interleukin
IND	Investigational New Drug
IV	Intravenous
SOC	Maximal Intensive Care
MERS	Middle East Respiratory Syndrome
MMRM	Mixed model repeated measures
RDR	Respiratory Distress Ratio
SOC	Standard of Care
SAE	Serious Adverse Events
SARS	Severe Acute Respiratory Syndrome
SARS-CoV-2	SARS-Coronavirus 2
TNF $\alpha$	Tumor Necrosis Factor Alpha
VIP	Vasoactive Intestinal Peptide

## 6. INTRODUCTION

### 6.1 Executive Summary

No therapeutic agent has demonstrated safety and efficacy in treating COVID-19 related Respiratory Failure. RLF-100™ (aviptadil) is a synthetic form of Vasoactive Intestinal Polypeptide (VIP), a ubiquitous, naturally synthesized human peptide binds to the Alveolar Type II (ATII) cell in the pulmonary epithelium and inhibits SARS-CoV-2 replication, blocks cytokine synthesis, inhibits cytopathy, and upregulates production of surfactant. The Coronavirus effect on the ATII cell causes the profound respiratory failure associated with COVID-19, perhaps precipitated by failure of surfactant production in the alveolus. RLF-100™ has been granted Fast Track designation for the treatment of COVID-19 Respiratory Failure by the FDA and admitted to the CoronaVirus Treatment Acceleration Program.

Aviptadil has a long history of human safety and has previously been granted investigational new drug (IND) status by the US FDA and the EMEA for treatment of Acute Respiratory Distress Syndrome (ARDS), Acute Lung Injury (ALI), Pulmonary Fibrosis, and Sarcoidosis. At least five well-controlled studies have been conducted for the use of aviptadil in chronic lung conditions.

VIP has demonstrated specific binding to pulmonary alveolar type II cells, which are the primary target of the SARS-CoV-2 virus. In the Type II cell, VIP upregulates surfactant production, inhibits SARS virus replication, inhibits cytokine production, and inhibits cytopathy in numerous non-clinical models of SARS infection, ARDS, and ALI. Aviptadil has shown early evidence of efficacy in preserving life in patients with ARDS. A phase 1 safety trial of aviptadil was conducted in eight patients with sepsis-related ARDS, who had an expected 50% mortality rate. Seven patients demonstrated clinical benefit based on improved blood oxygenation and were successfully withdrawn from advanced life support. Six of those patients survived long term and left the hospital, with one succumbing to an unrelated myocardial infarction post ICU discharge. These results demonstrate in a phase 1 study that aviptadil significantly reduced expected mortality in patients with ARDS (mortality reduction of  $p < .01$  vs historical controls). We propose RLF-100 (aviptadil) for the treatment of Critical COVID-19.

### 6.2 Definition of Critical COVID-19

In May 2020, FDA defined Critical COVID-19 to be used in clinical trials and disease staging as follows:

Critical COVID-19	

• Positive testing by standard RT-PCR assay or an equivalent test

• Evidence of critical illness, defined by at least one of the following:

○ Respiratory Failure defined on resource utilization requiring at least one of the following:

▪ Endotracheal intubation and mechanical ventilation, oxygen delivered by high-flow nasal cannula (heated, humidified, oxygen delivered via reinforced nasal cannula at flow rates <math>> 20</math> L/min with fraction of delivered oxygen <math>\geq 0.5</math>), noninvasive positive pressure ventilation, ECMO, or clinical diagnosis of respiratory failure (i.e., clinical need for one of the preceding therapies, but preceding therapies not able to be administered in setting of resource limitation)

○ Shock (defined by systolic blood pressure <math>< 90</math> mmHg, or diastolic blood pressure <math>< 60</math> mmHg or requiring vasopressors)

○ Multi-organ dysfunction/failure

--------------------------	--

Note that treatment with ECMO, mean arterial pressure  $< 65$  mmHg on pressors, and Multi-organ failure are exclusion criteria for this protocol

Acute Lung Injury in COVID-19 is characterized by progressive failure of corporeal oxygenation, attributed on large part by SARS-CoV-2 infection of Alveolar Type II cells (Mason 2020). Extensive nonclinical studies document that 70% of VIP in the body binds to VPAC1 receptors on the Alveolar Type II cell, where VIP is known to block cytokine production and upregulate production of surfactant.

The pathologic hallmark of COVID-19 lung injury is diffuse alveolar damage, vascular endothelium damage, and damage to the surfactant-producing type II cells which results in loss of the integrity of the

alveolar-capillary barrier, transudation of protein-rich fluid across the barrier, pulmonary edema, and hypoxemia from intrapulmonary shunting. Typically, patients who have progressed to Critical COVID-19 require care in an intensive care unit (ICU). The mortality rate is approximately 50%. Deaths usually result from multisystem organ failure rather than respiratory failure alone.

## 6.3 RLF-100 Experimental Therapy in COVID-19

Under this protocol, patients with Respiratory Failure associated with Critical COVID-19 will be randomly allocated to intravenous RLF-100™ (aviptadil), with the aim to support pulmonary alveolar function, combat the cytokine-induced inflammation, improve blood oxygenation, and reduce mortality.

## 6.4 Aviptadil Background

Aviptadil (vasoactive intestinal peptide; VIP) is an abundant biologically active peptide endogenous in humans as well as in other species. It is produced by neurons in the peripheral and central nervous system, by endocrine cells such as pituitary lactotrophs, cells of the endocrine pancreas as well as T-lymphocytes, and B-lymphocytes. This natural peptide is one of the signal molecules of the neuroendocrine-immune network comprising vasodilation, anti-proliferative, anti-inflammatory, and immuno-suppressive features. Aviptadil is predominantly localized in the lungs and a vast body of experimental, pharmacological as well as clinical evidence suggests Aviptadil to be an attractive candidate as a treatment option for acute pulmonary disorders.

Endogenous aviptadil is synthesized from a precursor molecule which contains 170 amino acids and is processed to its biologically active form via a signal peptidase in the endoplasmic reticulum and finally cleaved by prohormone convertases and by carboxypeptidase-B like enzymes to functional Aviptadil comprising the following 28 amino acids: His-Ser-Asp-Ala-Val-Phe-Thr-Asp-Asn-Tyr-Thr-Arg-Leu-Arg-Lys-Gln-Met-Ala-Val-Lys-Tyr-Leu-Asn-Ser-Ile-Leu-Asn.

Aviptadil was first identified in the intestine and then in the central and peripheral nervous systems and has since been recognized as a widely distributed neuropeptide, acting as a neurotransmitter and neuromodulator in many organs and tissues, including heart, lung, thyroid gland, kidney, immune system, urinary tract and genitals.

The widespread distribution of VIP is correlated with its involvement in a wide variety of physiological activities including smooth muscle relaxation, increased cardiac output, bronchodilation, immune-modulation, inhibition of smooth muscle cell proliferation, anti-apoptosis, neurotropic effects, and some differential effects on secretory processes in the gastrointestinal tract and gastric motility.

The rationale for the current application can be summarized as follows: VIP binds to and protects the specific cell (the Alveolar Type II cell) that is attacked by the SARS-CoV-2 virus in COVID-19. Once bound to the cell via the VPAC1 receptor, VIP blocks viral replication, increases surfactant production, blocks cytokine synthesis, and blocks cell death (cytopathy).

## 6.5 Clinical Rationale

Given by intravenous infusion in appropriate concentrations, aviptadil has been shown in clinical trials to have a manageable safety profile with no observed SAEs to date that would rise to the level of a black box warning. In an administratively-controlled trial of patients with COVID-19 respiratory failure and severe comorbidity (21 aviptadil-treated/24 controls), IV aviptadil dosed in 3 sequential infusions of 50/100/150 pmol/kg/hr was associated with a 9 fold increase in probability of recovery from respiratory failure and a comparable increase in survival over 60 days.

# 7. OBJECTIVES

## 7.1 Primary Objective

The primary objective of this study is to test the hypothesis that RLF-100 + maximal standard of care (SOC) shortens the time to respiratory failure resolution (see Section 6.2) in patients with Critical COVID-

19 compared to those treated with placebo + maximal SOC, in both cases not including ECMO.

## 7.2 Secondary Objective

The key secondary objective is to test the hypothesis that RLF-100 + maximal SOC improves NIAID Score over the first 28 (primary) and over the first 60 (secondary) days (from pre-treatment) in patients with Critical COVID-19 compared to those treated with placebo + maximal SOC, in both cases not including ECMO.

# 8. STUDY DESIGN

## 8.1 Overview

This study, RLF100-001, is a multi-center, randomized double-blind, placebo-controlled phase 2 trial, comparing RLF-100 + Maximal SOC to placebo + Maximal SOC. Aviptadil or placebo will be administered as a 12-hour IV infusion on three consecutive days. Patients with Critical COVID-19 infection will be screened. Informed consent will be obtained from the patient or a responsible party. Once entered into the study, participants will be randomized in a 2:1 ratio of IV RLF-100 + maximal SOC vs. placebo + maximal SOC. Once enrolled, patients assigned to receive RLF-100 will be given in three (3) doses of i.v. infusion, each dose given over 12-hour period at the same time on consecutive days, in escalating doses from 50pmol/kg/hr to 150 pmol/kg/hr of RLF-100. The primary outcome to be measured following RLF-100 infusion is the cumulative distribution of the time to respiratory failure resolution by 28 days with concurrent survival through 28 days. The declared secondary outcome to be measured following RLF-100 infusion will be the improvement in baseline for the NIAID Score from pre-treatment baseline to Day 28/exit using the remdesivir criterion (NIAID Score 6-8). Respiratory failure is defined as resource-based according to the FDA May 2020 respiratory failure definition (see Section 6.2). Eight other secondary efficacy endpoints are also to be evaluated in support of multi-dimensional efficacy.

## 8.2 Design

Randomized, prospective, double-blind, placebo-controlled trial of RLF-100 + maximal SOC vs. Placebo + maximal SOC therapy in patients with Critical COVID-19.

Following informed consent, patients will be randomized and administered either placebo or escalating doses of RLF-100 from 50 pmol/kg/hour IV to 150 pmol/kg/hour as three (3) 12 hour infusions each at the same time of day on subsequent study days 1, 2, and 3. Vital signs and telemetry will be monitored throughout the infusion and for 48 hours after completion of all 3 infusions. Pulmonary, cardiovascular, hepatic, CNS, renal, and coagulation functions will be assessed daily for 5 days, and plasma levels of aviptadil and selected cytokines will be measured.

The primary efficacy outcome is a pre-defined cumulative distribution of the time to respiratory failure resolution during the 28-day follow-up with concurrent survival. In other words, recovery from respiratory failure in the absence of survival to the end of the observation period is not considered treatment success. The cumulative distribution over the 28-day interval is consistent with the recent remdesivir approval. However, because the patients enrolled in this trial are exclusively those in category 6 and 7 of the remdesivir trial (where efficacy was not shown at 28 days), we will evaluate their key secondary efficacy endpoint (the percent achieving a NIAID Score 6-8 by Day 28/exit and by Day 60/exit).

Secondary outcome measures will include the cumulative distribution lifetable through Day 28 with attention paid to the Day 28 estimate from the lifetable. Time to ICU discharge, time on invasive mechanical ventilation, time on non-invasive ventilation, and time to discharge alive will be evaluated through Day 28. NIAID area under the curve (AUC) will be evaluated through Day 28.

Other outcome measures to be evaluated through Day 28 include the blood PaO2/FiO2 ratio (enrollment through extubation), oxygenation index, improvement in chest x-ray, IL-6, TNF $\alpha$  and other inflammatory markers.

[figure not shown]
The endpoint rationale is to include the traditional 28-day all-cause mortality plus clinically meaningful

endpoints indicative of multi-dimensional recovery.

## 8.3 Number of Participants

Initially, randomization will result in 14 participants to receive RLF-100 + SOC and 7 participants to receive placebo + SOC in the primary efficacy cohort comprised of patients who meet enrollment criteria and have been on mechanical ventilation for <8 days (including zero days for those not on mechanical ventilation). The total number of participants may expand to 198 patients (132 drug/66 placebo) if there are acceptable efficacy and safety profiles at the interim analyses. The analysis at 21 patients will be unblinded so this cohort will not be part of the final analysis but will be included in a supportive analysis since results remain confidential. Thus, the sample size for analysis purposes will be 198 patients for the primary analysis.

[figure not shown]

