## 10.7 Enrollment

The enrollment will be in accordance with a group sequential design. Up to 12 sites will participate.

The sample size for analysis purposes will be 198 patients (132 drug/66 placebo) for the primary analysis.

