## 14.5 Interim Analysis, Futility/Safety

Two pre-planned interim analyses will be conducted (n=21 initially, then an additional n=81). There will be 81% power and two-sided 5% overall Type I error to assess the primary endpoint with a total of 198 patients. The DSMB recommended that the sample size be increased to detect a smaller clinically meaningful difference for the primary efficacy endpoint (reduced from 25% to 22%).

The first interim analysis will be reviewed by the independent DSMB based on unblinded, unmasked data upon completion of 7-day data collection in the first 21 patients. DSMB meeting minutes will be recorded and provided to FDA. An unmasked/unblinded analysis will be performed for the independent DSMB in order to assess safety and efficacy. Safety determinations will entail a review of AEs and SAEs by the independent Data Safety and Monitoring Board in consultation with FDA. Based on this evaluation, the Sponsor will decide whether to permit adding additional study sites.

If the decision is made to continue the study, the next interim analysis will be performed once the next 81 patients complete the Day 28 evaluation for a safety and futility determination. As per FDA, the study will continue enrollment to 198 patients.

The details of the futility analysis follow. The futility analysis was conducted when 81 of the original 144 planned patients completed the study. If the conditional power, under the alternative hypothesis is less

than 10%, then the study will stop for futility.  $CP = \Phi(\mu\sqrt{1-t} + z_{1-p}\sqrt{\frac{t}{1-t} - \frac{z_{0.975}}{\sqrt{1-t}}})$ , where  $t = 81/144$  and  $p$  is the current corresponding one-sided p-value. The one-sided p-value to stop if the interim analysis occurs at exactly 81 patients will be 0.5949. This stop is non-binding and the DSMB will have the ability to continue if they see a positive signal in a secondary endpoint. This futility assessment will not spend any Type 1 error which will remain at 0.05.

The final sample size of 198 subjects (2:1 allocation favoring the RLF-100 group) is required to detect a 22% absolute increase in the percent with respiratory failure resolution by Day 28 for the RLF-100 group (assuming 62% success) and the SOC group (assuming 40% success) with 81% power and two-sided overall 5% Type 1 error accounting for the group sequential design using the Schoenfeld method.

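### Section 8.3 uses 198 both as the total that grows from the first 21 patients and as the number analysed once those 21 are removed, and no section gives a separate number to enrol or writes the exclusion into the mITT definition

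*Combined protocol and SAP*

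**What the plan says.** Section 8.3 opens with the first cohort: "Initially, randomization will result in 14 participants to receive RLF-100 + SOC and 7 participants to receive placebo + SOC". It goes on: "The total number of participants may expand to 198 patients (132 drug/66 placebo"), if efficacy and safety are acceptable at the interim analyses. Because the look at 21 patients is unblinded, "this cohort will not be part of the final analysis but will be included in a supportive analysis since results remain confidential". The section then concludes: "Thus, the sample size for analysis purposes will be 198 patients for the primary analysis".

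Elsewhere the same figure appears in different roles:

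- Synopsis, under a heading for the total participant number: "198 evaluable (mITT) subjects with Critical COVID-19 on mechanical ventilation". The Synopsis sample size paragraph also attaches 198 to the primary analysis group.
- Section 10.7: "The sample size for analysis purposes will be 198 patients (132 drug/66 placebo) for the primary analysis". This is the same 132/66 split that 8.3 gives for the total.
- Section 14.5: "As per FDA, the study will continue enrollment to 198 patients". The same section ties the 81% power to a total of 198.
- Section 14.3 defines the mITT population by removing untreated and ineligible patients only. Final membership is settled at a data review meeting at study completion. Section 15.1 runs the primary test on all mITT patients.

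**The concern.** One number cannot be both a total that includes the first 21 and the count left after they are taken out. The plan therefore does not say when enrolment ends. A sponsor who stops at the total in 8.3 and 14.5 and then applies the exclusion in 8.3 would analyse 21 fewer patients than the sample size statement describes, 7 of them from only 66 planned controls.

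The analysis set has a related gap. The exclusion of the 21 appears only in 8.3. Sections 14.3 and 15.1, read alone, would admit 21 patients whose data have already been analysed unblinded. Whether they enter the primary test should be fixed in the population definition, not left to a meeting at the end of the study.

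**Working it through.** **Counts.** Inputs: first cohort 21 = 14 + 7 (8.3); 198 = 132 + 66 (8.3, 10.7).

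| Reading | Treated and eligible patients needed | Primary analysis set |
|---|---|---|
| 21 inside a total of 198, then removed | 198 | 198 − 21 = 177 (132 − 14 = 118; 66 − 7 = 59) |
| 21 additional to the 198 | 198 + 21 = 219 (132 + 14 = 146; 66 + 7 = 73) | 198 (132/66) |
| Total of 198, 14.3 applied as written | 198 | 198 including the 21, contrary to 8.3 |

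The shortfall in the first reading is 21/198 = 10.6%. No section states 219.

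**Power inputs.** 40% against 62% success by Day 28, two-sided 5%, 2:1 allocation, 81% power (Synopsis and 14.5). Section 14.2 prints 50% for RLF-100 beside a 22-point difference. I used 62% because the Synopsis and 14.5 agree on it. No dropout is assumed (13.4 expects none).

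**Formulas.**

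- Scaling the stated power: 81% corresponds to z = 0.878, so power at 177 is Φ((1.960 + 0.878) × √(177/198) − 1.960) = Φ(0.723) = 76.5%.
- Schoenfeld log-rank under proportional hazards: HR = ln(0.60)/ln(0.38) = 0.528 (14.2 gives 0.52). Power = Φ(√(events × 1/3 × 2/3) × |ln HR| − 1.960). Events at 198: 132 × 0.62 + 66 × 0.40 = 108.2. Events at 177: 118 × 0.62 + 59 × 0.40 = 96.8.
- Pooled two-proportion test: Φ((0.22 − 1.960 × SE0)/SE1), where SE0 uses the pooled rate and SE1 the separate rates. At 198, SE0 = 0.0750 and SE1 = 0.0736. At 177, SE0 = 0.0794 and SE1 = 0.0779. The continuity-corrected form also subtracts (1/n0 + 1/n1)/2 from the difference, where n0 and n1 are the group sizes.
- Fisher exact: enumeration over both binomial distributions.
- Simulated log-rank: exponential times, everyone without an event by Day 28 censored there, 4,000 runs.

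| Method | 198 (132/66) | 177 (118/59) | Loss (points) |
|---|---|---|---|
| Stated 81%, scaled | 81.0% | 76.5% | 4.5 |
| Fisher exact, Day 28 | 82.3% | 76.1% | 6.2 |
| Two proportions, continuity-corrected | 79.8% | 74.7% | 5.1 |
| Two proportions, pooled | 83.9% | 79.6% | 4.3 |
| Log-rank, simulated | 85.2% | 80.1% | 5.1 |
| Schoenfeld, HR 0.528 | 88.0% | 84.2% | 3.8 |
| Schoenfeld, HR 0.52 | 89.4% | 85.8% | 3.6 |

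The plan's 81% at 198 is matched within two points by the Fisher and continuity-corrected comparisons of Day 28 proportions. The Schoenfeld log-rank method that the plan names gives more. The Freedman form of the log-rank formula moves from 78.5% to 73.8%, or from 92.2% to 89.1%, depending on direction.

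**The case against.** The strongest reply is that 198 always means analysed patients and that 8.3 is only loosely worded. Much of this stands:

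- The Synopsis calls the 198 evaluable mITT patients and places them in the primary analysis group. Section 10.7 also speaks of an analysis number.
- Section 14.5 counts the second look from the 81 patients after the first 21, and sets the information fraction at 81/144. Had the 144 included the 21, only 144 − 21 = 123 would have been available for the final analysis, and the fraction would have been 81/123.
- Sampling stops after 165 evaluable patients (15.12, 16.10, Appendix A). That equals 144 + 21, although the plan does not explain the figure.

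This makes 219 the likelier intent, but it remains an inference. The sentence in 14.5 that governs enrolment says 198. If 165 does mean 144 + 21, then the first 21 were counted as evaluable there, so the word in the Synopsis cannot be relied on to exclude them.

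A reader might also infer three stronger things that the documents do not support:

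- **The trial will fall short of 81% power.** The loss arises only if enrolment stops at 198 and the 21 are removed. Even then, the named Schoenfeld calculation stays above 81%, and the simulated log-rank result of 80.1% is close to it.
- **Fewer than 177 would be analysed.** That needs 198 to be a raw enrolment cap and some patients to be untreated or ineligible. The Synopsis states 198 as mITT, already net of both.
- **The plan intends the unblinded 21 to enter the primary test.** Section 8.3 says the opposite. Section 14.3 merely fails to carry the exclusion through.

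**Conclusion.** The inconsistency is real: 8.3 gives 198 two incompatible meanings, 14.5 repeats it as an enrolment figure, and 14.3 does not contain the exclusion. It is a defect in how enrolled and analysed numbers are stated, and does not show that the trial is underpowered.

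The size is conditional. On the likelier reading (219 treated and eligible, 198 analysed) nothing is lost. If enrolment stops at 198 in total and the 21 are removed, 177 (118/59) are analysed, 10.6% fewer, at a cost of about 4 to 6 points of power on the tabulated methods. Whether power then falls below 81% depends on the method: it does for the Day 28 proportion tests and for the scaled figure, and it does not for Schoenfeld's log-rank formula at about 84%. These figures assume 40% against 62%, 2:1 allocation, no dropout and, for the log-rank results, proportional hazards. The point should be corrected, because it fixes both the end of enrolment and the primary analysis set.

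**What to change.** In the Synopsis, 8.3, 10.7 and 14.5, state enrolled and analysed numbers separately and choose one of two rules:

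1. Enrolment ends when 198 mITT patients (132/66) randomised after the first 21 have been treated, which is 219 (146/73) treated and eligible patients overall.
2. The total is 198, the primary analysis set is 177 (118/59), and the power is restated for 177 with the method named.

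Under either rule, add to 14.3 that the first 21 patients are excluded from the primary mITT set and enter only the supportive analysis. Without that line, correcting the counts would still leave a population definition that admits them.

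The cost is wording in five places. If 219 was always intended, no patients are added. If enrolment was to stop at 198, the cost is either 21 more patients or a restated power for the smaller set.
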